#### 4.1.2. Subject Replacement

A subject who is withdrawn from the study before the completion of the first 21 days for a reason other than a DLT or who receives less than 16 of 21 doses of GS-4224 in the first 21 days will be replaced.

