### **5.3. Dosage and Administration of GS-4224**

The GS-4224 study drug will be supplied as tablets in strengths of 100 mg, 200 mg, and/or 500 mg. GS-4224 will be taken once daily in the morning (400 1500 mg QD cohorts) and 1000 mg twice daily separated by approximately 12 hours (1000 mg BID cohort).

On days with intensive PK (Cycle 1 Days 1 and 15), study drug will be administered at the same time every morning with approximately 240 mL of water and following an overnight fast (no food or drinks, except water, for at least 8 hours). For study treatments including those of more than 5 tablets, up to an additional 120 mL of water can be administered, if necessary. Water will be withheld starting 1 hour before and for 2 hours after dose administration, except for water given with the study drug. Water may be consumed by subjects following the 2-hour blood draw for the remainder of the collection period. A meal (standardized lunch) will be provided to subjects after the 4 hour postdose blood draw. All other fluids will be allowed after the 4 hour postdose blood draw.

For all days that study drug is administered where no intensive PK assessments are required, GS-4224 should be administered without regard to food at approximately the same time every morning. Subjects should administer study drug with a full glass of water.

If vomiting occurs after administration of study drug, the dose should not be repeated.

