#### 8.3.1.4. DLT-Evaluable Analysis Set

The DLT-Evaluable Analysis Set includes all subjects in the Safety Analysis Set who enroll to the dose escalation cohorts (up to the first 6 subjects in the 1000 mg BID dose escalation cohort; CCI [REDACTED]), complete  $\geq 75\%$  of the prescribed study treatment and have safety assessments through the protocol-specified DLT assessment window (first 21 days of study dosing, inclusive) or have experienced a DLT prior to the completion of first 21 days of study dosing. Safety assessment relevant to the DLT-Evaluable Analysis Set definition will include laboratory serum chemistry tests and hematology tests as specified in the protocol. Determination of the MTD will be based on the DLT-Evaluable Analysis Set.

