3.1.4. DLT-Evaluable Analysis Set

The DLT-Evaluable Analysis Set includes all subjects in the Safety Analysis Set who enroll to the dose escalation cohort (excluding the Dose Escalation Biopsy Substudy), complete $\geq 75\%$ of the prescribed study treatment (ie., at least 16 of 21 doses) and have safety assessments through the protocol specified DLT assessment window (first 21 days of study dosing, inclusive) or have experienced a DLT prior to the completion of first 21 days of study dosing. Safety assessment relevant to the DLT-Evaluable Analysis Set definition will include laboratory serum chemistry tests and hematology tests as specified in the protocol. Determination of the MTD will be based on the DLT-Evaluable Analysis Set.

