4.2.1. Extent of Exposure to Study Drug

Total duration of exposure to study drug GS-4224 will be defined as last dosing date of study drug minus first dosing date plus 1, regardless of any temporary interruptions in study drug administration, and will be expressed in weeks using up to 1 decimal place (eg, 4.5 weeks). If the last study drug dosing date is missing,

- If the study drug is permanently withdrawn, the latest date among the study drug end date, clinical visit date, laboratory sample collection date, and vital signs assessment date that occurred during the on-treatment period will be used for subjects included in the final analyses or the last available date in the database snapshot for subjects who were still on treatment at the time of an interim analysis.
- If the study drug completion status is unknown, the earlier of the date of death or data cut-off date for analysis will be used.

The actual duration of exposure to GS-4224 during the DLT assessment window is defined as the last dosing date minus first dosing date plus 1 within the DLT assessment window (first 21 days of study drug dosing), taking into account investigator-prescribed dose interruptions in study drug administration within the DLT assessment window. The level of prescribed adherence to the study drug GS-4224 during the DLT assessment window will be determined by the actual duration of exposure to GS-4224 relative to the total duration of exposure specified by study protocol during a subject's DLT assessment window.

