4.2.2. Adherence to Study Drug

The level of prescribed adherence during the DLT assessment window will be expressed as a percentage using the following formula:

Prescribed Adherence During DLT Assessment Window (%) =

$$= \frac{\text{Actual Duration of Exposure to Study Drug During DLT Assessment Window}}{\text{Total Duration of Exposure Specified by Protocol During DLT Assessment Window}} \times 100$$

Descriptive statistics for the level of prescribed adherence with the number and percentage of subjects belonging to adherence categories (eg, < 75%, ≥ 75%) will be provided by cohort for the Safety Analysis Set.

A by-subject listing of study drug (GS-4224) administration will be provided by cohort and subject ID number (in ascending order), including dosing date, total duration of exposure to GS-4224, actual duration of exposure, the prescribed adherence during the DLT assessment window, and reason for dose interruption.

The total duration of exposure to study drug will be summarized using descriptive statistics and using the number (ie, cumulative counts) and percentage of subjects exposed through the following time periods: 1 day, 3 weeks, 6 weeks, 9 weeks, 12 weeks, 18 weeks, and 24 weeks. Summaries will be provided by cohort for the Safety Analysis Set.

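### The SAP's dose count for DLT evaluability fits once-daily dosing only: 16 doses is 38% of the 42 planned in the 1000 mg BID cohort, and the adherence table does not count doses taken

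*SAP*

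**What the plan says.** **Evaluability.** Protocol 8.3.1.4 requires at least 75% "of the prescribed study treatment and have safety assessments through the protocol-specified DLT assessment window", or a DLT before the window closes, and gives no dose count. It adds: "Determination of the MTD will be based on the DLT-Evaluable Analysis Set". SAP 3.1.4 repeats the percentage but explains it with a count, "of the prescribed study treatment (ie., at least 16 of 21 doses", and does not separate the dosing schedules.

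**Replacement.** Under protocol 4.1.2 a subject "who receives less than 16 of 21 doses of GS-4224 in the first 21 days will be replaced". This rule uses the same count, with no percentage and no distinction by schedule.

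**Schedule.** The top dose level takes "1000 mg twice daily separated by approximately 12 hours (1000 mg BID cohort" (protocol 5.3). It is one of the five levels in SAP 1.2.1.

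**Adherence.** SAP 4.2.1 defines actual exposure in the DLT window as last dosing date minus first dosing date plus 1, "taking into account investigator-prescribed dose interruptions in study drug administration within the DLT assessment window". SAP 4.2.2 divides this by the protocol-specified duration and tabulates the "number and percentage of subjects belonging to adherence categories", with below 75% and at least 75% as the example categories.

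**Protocol exposure summaries.** Protocol 8.7.1, which sits within Safety Analysis, plans summaries of doses prescribed, doses taken, duration, and the number and timing of interruptions, plus compliance by returned pill count. SAP 4.2 covers total duration, actual duration and prescribed adherence, with a by-subject administration listing. SAP 7.7 states that the protocol's safety analyses are unchanged.

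**The concern.** The DLT-Evaluable set decides the MTD, and determining the MTD or RP2D remains a primary objective in the SAP. At least 6 treated subjects are needed before a level can be called the MTD, so membership matters subject by subject. For the BID cohort, SAP 3.1.4 gives a percentage and a count that cannot both be applied, and a programmer has no basis for choosing between them. Because replacement follows the count and protocol evaluability follows the percentage, a BID subject could be neither replaced nor evaluable.

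The adherence table uses the same 75% cut, so a reader of the CSR may take it as evidence that subjects met the evaluability rule. It cannot serve as that evidence if it does not reflect doses the subject missed. The dose-count and pill-count summaries that would have shown this are the ones left out.

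**Working it through.** **Inputs.** DLT window: 21 days (SAP 7.1.7). Doses per day: 1 for QD, 2 for BID (protocol 5.3). Threshold: 75% (protocol 8.3.1.4, SAP 3.1.4). Stated count: 16 of 21 (SAP 3.1.4, protocol 4.1.2). The BID total is derived, not printed: 2 × 21 = 42.

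**Step 1: the count.** Minimum doses = 0.75 × planned doses, rounded up.

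| Schedule | Planned doses | 75% of planned | Minimum count | Share at minimum | Share at 16 doses |
|---|---|---|---|---|---|
| QD | 21 | 15.75 | 16 | 16/21 = 76.2% | 76.2% |
| BID | 42 | 31.5 | 32 | 32/42 = 76.2% | 16/42 = 38.1% |

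The plan's figure reproduces exactly for QD and not for BID. Since 31/42 = 73.8%, the two criteria disagree for BID from 16 to 31 doses (38.1% to 73.8%). A subject in that band without a DLT:

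- is not replaced under protocol 4.1.2 (at least 16 doses);
- is not evaluable under protocol 8.3.1.4 (below 75%);
- under SAP 3.1.4 passes the count and fails the percentage.

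Reading the count as dosing days does not settle it. Sixteen days with both doses is 32/42 = 76.2%, but sixteen days with one dose each is 16/42 = 38.1%.

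**Step 2: the adherence formula.** I read the SAP 4.2.1 adjustment as a deduction of prescribed interruption days:

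adherence = (last date − first date + 1 − prescribed interruption days) / 21 × 100.

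With a first dose on Day 1, a last dose on Day 21 and no prescribed interruption, this is (21 − 1 + 1)/21 = 100%, whatever was missed in between.

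| Pattern | Doses taken | SAP score |
|---|---|---|
| QD, 6 unprescribed skips | 15/21 = 71.4% | 100% |
| QD, only Days 1, 2, 4, 8, 11, 15 (the Cycle 1 visits in protocol Appendix 2) and Day 21 taken: 14 skips | 7/21 = 33.3% | 100% |
| BID, all morning doses taken, 11 evening doses missed | 31/42 = 73.8% | 100% |
| BID, all evening doses missed | 21/42 = 50.0% | 100% |

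So a QD subject can skip 6 to 14 doses and a BID subject 11 to 21 evening doses, fall below 75% of planned doses, and still be tabulated at or above 75%. The documents give no likelihood for these patterns.

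**Step 3: planned against listed summaries.**

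| Protocol 8.7.1 | SAP 4.2 |
|---|---|
| Doses prescribed | Not summarized |
| Doses taken | Not summarized |
| Pill-count compliance | Not summarized |
| Number and timing of interruptions | No summary; reason for interruption listed by subject |
| Duration of exposure | Summarized |

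SAP 7.7 records none of these omissions.

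**The case against.** The best defence of SAP 3.1.4 is that the operative rule is the percentage, which is correct for BID; the bracketed count is a leftover from once-daily dosing, and its denominator of 21 is one a BID subject does not have. Meant as days with both doses taken, it would agree with 75%. This lowers the weight of the point but does not remove it: the text says doses, the dosing-days reading does not guarantee 75%, and protocol 4.1.2 uses the count alone.

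No consequence is demonstrated. The study stopped early in Phase 1b, the documents do not say whether anyone was treated at 1000 mg BID, and a subject with a DLT is evaluable regardless of doses taken. That stands.

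The adherence table is labelled as prescribed adherence and measures what the label says. SAP 3.1.4 does not refer to SAP 4.2, so misclassification in the evaluable set itself is not shown. Diary accountability at every Cycle 1 visit would probably expose gross non-adherence, and the SAP 4.2.2 listing may show some cases, although the detail of its dosing dates is not stated. All of this is fair. What remains is a table that shares the evaluability cut without measuring doses taken, and no other SAP summary that does.

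A synoptic CSR may justify fewer exposure tables. It does not make the SAP 7.7 statement accurate, and SAP 2.1.2 and 2.1.3 do record other analyses dropped because of early termination. This third part is a matter of disclosure, not an analysis flaw.

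**Conclusion.** The concern holds in all three parts. The dose count in SAP 3.1.4 is wrong as an expression of 75% for the BID cohort: it corresponds to 38.1%, and the two criteria conflict from 16 to 31 of 42 doses. The DLT-window adherence table can show 100% for subjects who took well under 75% of planned doses. The dose-count and pill-count summaries are missing without being declared.

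This should be corrected before the CSR relies on the set or the table. I claim no effect on the MTD and no direction of bias. The arithmetic rests on two doses on each of 21 days; the practical effect depends on whether BID subjects were enrolled and how many doses they missed, and the documents state neither.

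**What to change.** 1. In SAP 3.1.4, mark 16 of 21 as applying to QD cohorts only; the plan's own 75% corresponds to 32 of 42 for BID. Protocol 4.1.2 and 8.3.1.4 must be reconciled for BID so that replacement and evaluability do not conflict. If a protocol amendment is no longer practical after early termination, state in the CSR how each rule was applied.
2. Use one derivation for both the evaluability flag and the adherence table: doses taken divided by doses planned in the window (21 QD, 42 BID), from diary and accountability data where recorded. Where they are not recorded, keep the present measure and footnote that it does not reflect missed doses without a prescribed interruption.
3. Restore the protocol 8.7.1 dose-count and pill-count summaries, or declare their omission in SAP 7.7 or the CSR. The same applies to the number and timing of interruptions.

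The cost is wording in SAP 3.1.4 and 7.7, one derivation and, if restored, a few exposure tables. SAP section 1 already allows later changes to be documented in the CSR. The derivation assumes dose-level diary data are in the database: protocol Appendix 2 schedules diary accountability but not how it is recorded, and pills returned at C2D1 (±2 days) may not isolate Days 1 to 21. Reported adherence may come out lower.

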3.1.5. Pharmacokinetics (PK) Analysis Set

The PK Analysis Set includes subjects in the Safety Analysis Set who have received the study drug and have at least 1 sample with detectable drug concentration.

3.2. Subject Grouping

For analyses based on the Full Analysis Set[FAS], subjects will be grouped according to the treatment to which they were randomized. For analyses based on the Safety Analysis Set, subjects will be grouped according to the actual treatment received. The actual treatment received will differ from the randomized treatment only when their actual treatment differs from randomized treatment for the entire treatment duration.

For the PK Analysis Set, subjects will be grouped according to the actual treatment they received.

For a subject with intra-patient dose escalation per study protocol, the subject will be grouped under the original enrolled cohort in summary tables, unless otherwise specified.

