**Treatment:**

Subjects who meet eligibility criteria will receive GS-4224 orally once daily in the 400 1500 mg QD cohorts and 1000 mg twice daily in the 1000 mg BID cohort (separated by approximately 12 hours). Each cycle will consist of 21 days. Safety and efficacy assessments will occur on an outpatient basis including assessment of tumor response, physical exam, vitals, ECG, collection of blood samples (for routine safety labs, GS-4224 PK, pharmacodynamic markers, and other biomarkers at applicable visits), urine pregnancy test (every 3 weeks while receiving GS-4224 in females of childbearing potential), and assessment of AEs. In addition, subjects will undergo postbaseline CT/MRI and PET-CT (for cHL) scans for tumor response assessment. A subject who does not show evidence of disease progression by clinical assessment or by CT/MRI or applicable scan may continue receiving study treatment until disease progression (clinical or radiographic), unacceptable toxicity, withdrawal of consent, or other reasons specified in Section 3.5.

After discontinuation of all study treatment, subjects will be followed for safety for 30 days.

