### **5.4. Dose Modifications and Treatment Interruption of GS-4224**

#### **5.4.1. Dose Modifications**

For Dose Escalation 400 1500 mg QD cohorts, after completing 4 cycles of treatment and C5D1 scans, subjects receiving GS-4224 at a dose level below that which has been deemed to be safe by the SRT may, at the investigator's discretion, receive GS-4224 at the highest dose deemed to be safe by the SRT. **CCI**

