p Where required for enrollment and if not already known, PD L1 expression will be determined.  
q Archival tumor tissue for biomarker analysis will be collected. The tissue should preferably be obtained either at the time of or after the diagnosis of advanced disease has been made and from a site not previously irradiated. Tissue must be collected between screening and Cycle 2. If archival tissue is not available, a pre treatment biopsy will be collected from enrolled subjects. For the 1000 mg BID dose escalation cohort, subjects with melanoma, Merkel cell, MSI H cancers, and classical Hodgkin lymphoma are not required to have archival or fresh biopsy tissue

[REDACTED]

t Tumor evaluation by CT/MRI will be performed during screening (within 28 days of Day 1) and every 6 weeks for the first 2 scans and then every 9 weeks. A baseline scan within 6 weeks of Day 1 is acceptable. Cycle 3 Day 1 and Cycle 5 Day 1 scans can have a 7 day window. The same radiographic procedure used to define measurable lesions must be used throughout the study for each subject.  
u PET CT to be completed at screening (within 28 days of Day 1), Cycle 3 Day 1, and Cycle 5 Day 1 only for subjects with cHL. Per Lugano 2014 criteria, PET CT is required to confirm radiographic CR in subjects with bone marrow involvement at screening. In subjects with bone marrow involvement at screening and at a time point where CR is suspected, PET CT will be required to confirm CR if CR was not achieved at Cycle 3 and/or 5.

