1. INTRODUCTION

This statistical analysis plan (SAP) describes the statistical analysis methods and data presentations to be used in tables, figures, and listings (TFLs) in the clinical study report (CSR) for Study GS-US-494-5484. This SAP is based on the study protocol amendment 5.0 dated 02 October 2020 and the electronic case report form (eCRF). The SAP will be finalized before database finalization. Any changes made after the finalization of the SAP will be documented in the CSR.

The study was originally designed to evaluate the safety, tolerability, Pharmacokinetics (PK), and efficacy of GS-4224 monotherapy in 2 stages: (1) Phase 1b dose-escalation in advanced solid tumors; and (2) Phase 2 dose expansion in select advanced solid tumors expressing ligand 1 of programmed cell death protein 1 (PD-L1) [tumor proportion score (TPS) \geq 1% or combined positive score (CPS) \geq 1 or \geq 10] or MSI-H cancers. The study was early terminated during Phase 1b dose escalation part due to lack of objective clinical efficacy in patients dosed in Phase 1b dose-escalation. The Phase 2 part of the study was not be initiated. Subjects currently on study will continue to be treated and/or followed until the end of study criteria are met. The SAP describes the analyses based on the Phase 1b data collected in the study only for a synoptic CSR.

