1.1. Study Objectives

1.1.1. Primary Objectives

Phase 1b Dose Escalation

- To characterize the safety and tolerability of GS-4224 in subjects with advanced solid tumors
- To determine the maximum tolerated dose (MTD) or recommended Phase 2 dose (RP2D) of GS-4224 in subjects with advanced solid tumors

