7.1.5. Treatment-Emergent Adverse Events

7.1.5.1. Definition of Treatment-Emergent Adverse Events

Treatment-emergent adverse events (TEAEs) are defined as 1 or both of the following:

- Any AEs with an onset date on or after the study drug start date and no later than 30 days after permanent discontinuation of study drug
- Any AEs leading to permanent discontinuation of study drug.

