7.1.6. Summaries of Adverse Events and Deaths

TEAEs will be summarized by cohort/dose level based on the Safety Analysis Set.

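### Does keeping escalated subjects in their enrolled cohort put late safety data under the wrong dose?

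*SAP*

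**What the plan says.** Protocol 5.4.1 applies to the 400 to 1500 mg QD cohorts. Once four cycles and the C5D1 scans are complete, the investigator may choose to have a subject "receive GS-4224 at the highest dose deemed to be safe by the SRT". The visible text then runs into a redaction, so further conditions may exist. On timing, the Protocol Synopsis (Treatment) states "Each cycle will consist of 21 days", and the imaging footnote to Protocol Appendix 2 adds "Cycle 3 Day 1 and Cycle 5 Day 1 scans can have a 7 day window".

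SAP 3.2 sets the grouping for these subjects: "the subject will be grouped under the original enrolled cohort in summary tables, unless otherwise specified". The outputs that could be affected are:

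- **Adverse events** (SAP 7.1.6): "TEAEs will be summarized by cohort/dose level based on the Safety Analysis Set". Under SAP 7.1.5.1 events count if their onset is "no later than 30 days after permanent discontinuation of study drug".
- **Deaths** (SAP 7.1.6.2): by cohort.
- **Laboratory abnormalities** (SAP 7.2.1.1 and 7.2.1.2): by test and cohort, worst grade up to 30 days after the last dose.
- **Exposure duration** (SAP 4.2.2): by cohort, as cumulative counts of subjects exposed through seven time points from 1 day to 24 weeks.

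The SAP also makes specific provision for escalated subjects. SAP 7.1.6.1 plans a separate adverse event listing for them, and SAP 3.8.1 says it will show days counted from the first dose at each level.

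**The concern.** The first primary objective is "To characterize the safety and tolerability of GS-4224 in subjects with advanced solid tumors". In a dose-escalation study a reader expects a column headed with a dose to describe that dose. If a subject enrolled at a low dose escalates and then has a severe event, the table shows it in the low-dose column. Follow-up is not cut at escalation, and SAP 1 confirms continued dosing after the early termination: "Subjects currently on study will continue to be treated and/or followed until the end of study criteria are met". Columns may hold only three to six subjects, so one event is visible. The dedicated listing covers adverse events only, and the drug-administration listing in SAP 4.2.2 does not name dose level among its contents. It could seem, then, that late deaths and laboratory grades cannot be tied to the dose actually taken.

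**Working it through.** The plan states no figure on this point, so the check is day arithmetic followed by a reading of each output.

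**When escalation can start.** Four cycles of 21 days give 4 × 21 = 84 days, so C5D1 is nominally Day 85. The ±2-day visit window in Protocol Appendix 2 gives Days 83 to 87. A scan 7 days late gives 85 + 7 = Day 92.

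**What precedes it.**
- The DLT window ends on Day 21. DLT incidence and the MTD are unaffected.
- PK parameters come from Cycle 1 Days 1 and 15 (SAP 8). They are unaffected.
- The RP2D is to consider toxicities through 90 days (Protocol 3.2.1.2). The overlap with escalated dosing is at most 90 − 85 + 1 = 6 days from nominal C5D1. Phase 2 was not started, and SAP 2.1.2 says the dose-expansion analysis will not be done.

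**Exposure table.** Week 12 ends on Day 84, Week 18 on Day 126 and Week 24 on Day 168. A subject escalated on Day 85 has 126 − 84 = 42 of 126 days (33%) at the higher dose by Week 18, and 168 − 84 = 84 of 168 (50%) by Week 24. With a C5D1 visit on Day 83, two days could fall inside Week 12. These shares describe one subject's dosing history. The planned statistic counts subjects still exposed at each time, and that count is correct whatever dose they are taking.

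**How far the label could differ from the dose taken.** Assume that 1000 mg BID (2000 mg/day) was the highest dose cleared. The ratios to the enrolled daily dose are 2000/400 = 5.0, 2000/700 = 2.9, 2000/1000 = 2.0 and 2000/1500 = 1.3. Over all upward steps in the schema, the ratio runs from 1.3 to 5.0.

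**How far a rate could move.** Assume that one subject's only qualifying event follows escalation. It adds 1/3 = 33 points to a column of three, or 1/6 = 17 points to a column of six. It is nevertheless an event that a member of that enrolled cohort really had, so the percentage is correct for the group the column names. Pooled biopsy-substudy subjects (SAP 1.2.1) would make the shift smaller.

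**Can dose at the event be recovered?**
- *Adverse events:* yes, directly, from the listing described in SAP 3.8.1 and 7.1.6.1.
- *Deaths:* all are listed by subject (SAP 7.1.6.2). An escalated subject was alive at escalation, so any such death follows it, and dosing dates identify the last period on drug.
- *Laboratory grades:* every result is listed chronologically by subject, with graded values flagged (SAP 7.2).
- *Dosing:* the administration listing gives dosing dates. Its contents are introduced as inclusions rather than a closed list, so a dose column is not ruled out.

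**The case for a change.** The strongest argument for a change is that the SAP recognises that dose at onset matters, since it plans a listing for it, and then stops at adverse events. SAP 3 labels the listings with the initially assigned cohort, so death and laboratory listings carry the original dose too. Deaths from unrelated disease progression are exempt from serious adverse event reporting (Protocol 7.1.2.1), so they may not appear in the adverse event listing. Protocol 8.7 plans safety summaries by cohort, indication and treatment, while the SAP's death and laboratory tables use cohort only and SAP 7.7 declares no deviations. The phrasing of SAP 7.1.6 could be taken to mean dose at onset.

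Part of this stands. For deaths and laboratory grades the dose must be cross-read from two listings, and the SAP does not promise a dose column. The rest is weaker. The protocol nowhere defines treatment as dose at onset. Phase 1b cohorts are named by their dose levels (SAP 1.2.1), so the two terms in SAP 7.1.6 read as synonyms, and that section gives nothing that displaces the default in SAP 3.2.

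A before-and-after table for escalated subjects would add little. The group is selected for at least 12 weeks on treatment, so it is not comparable with subjects who started at the higher dose. Protocol 5.4.3 warns that immune-related events can appear months after the last dose, so dose at onset does not settle attribution. For a handful of subjects, the by-subject listing says more and misleads less.

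**Conclusion.** The observation is accurate, but it does not call for a change to the plan. Grouping by enrolled cohort is a disclosed convention and a fair trade-off: it keeps each subject in one column with one denominator, and a listing shows adverse event timing by dose level. No planned number is wrong as defined. DLT incidence, the MTD, the Cycle 1 PK results and the exposure counts are unaffected, and no formal testing is planned (SAP 3.5).

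What is left is an inconvenience for deaths and laboratory grades after about Day 85 (Day 83 to Day 92 with the visit and scan windows), in subjects who escalated. Their number is not given and may be zero, and the redacted end of Protocol 5.4.1 may narrow it further. A count of escalated subjects under the affected tables and a dose column in the administration listing are ordinary choices when output shells are drawn up, and the SAP as written allows both.

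This conclusion assumes that dosing dates and dose changes are recorded by subject, as the per-level day calculation in SAP 3.8.1 requires, and that the tables stay descriptive and are used only for the synoptic report.
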